2. ECG
3. Procedures:
  - a) FeNO
  - b) Spirometry (FEV1) and Reversibility
  - c) Electronic Diary download
4. Safety and laboratory assessments
5. Administration of IMP

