8.2 Noninvestigational medicinal products, 8.8 Concomitant Medication	Specify that the third controller is not allowed for an additional 4 weeks prior to screening visit (V1).	To clarify time window required between the third controller withdrawal and the screening visit V1.
8.8 Concomitant Medication	Remove intra-articular steroids from permitted concomitant therapy	Resolve an inconsistency as relevant systemic exposure may occur with intra-articular steroids. Systemic steroids (except systemic steroids to treat asthma exacerbations) are not permitted during the screening or treatment phases.
9.2.2.5 Standardized Rhinoconjunctivitis Quality of Life Questionnaire in those patients with comorbid allergic rhinitis	Corrected from Rhinoconjunctivitis Quality of Life Questionnaire (RQLQ[S] +12) to RQLQ[S]	To fix discrepancy between the Appendix F and section 9.2.2.5. RQLQ [S] is the questionnaire intended to be used in the study since only adult patients can participate in the study. Section 9.2.2.5 incorrectly mentions the RQLQ[S] +12 questionnaire that is intended for adults and kids of age $\geq 12$ .
9.3.1.1 Sampling time, 10.6.4 Elevated liver function tests	Specify that ADA sampling should only be performed for SAEs and AESIs of anaphylaxis, hypersensitivity reaction, injection site reaction	To harmonize with other SAR440340 studies. It is anticipated that formation of ADA will likely have limited effect on liver function.

Section # and Name	Description of Change	Brief Rationale
	but not in case of liver ALT increase	
9.3.2.1 Pharmacodynamic variables	Serum (not plasma) will be collected for testing Pulmonary and activation-regulated chemokine (PARC)	Serum will be used to assay for PARC
10.1 Visit Schedule	Change the order of assessments (ECG positioned prior to lung function measurements).	All ECGs should be preferably performed prior to FeNO and spirometry measurements in order to prevent potential effect of albuterol/salbutamol/levalbuterol/levosalbutamol administration on ECG tracing.

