- n* Hematology will include hemoglobin, hematocrit, platelet count, total white blood cell count, differential count, and total red blood cell count. Serum chemistry will include creatinine, blood urea nitrogen, glucose, uric acid, total cholesterol, total protein, albumin, total bilirubin, alanine aminotransferase, aspartate aminotransferase, alkaline phosphatase, electrolytes (sodium, potassium, chloride), bicarbonate, and creatine phosphokinase. Urinalysis will include specific gravity, pH, glucose, ketones, blood, protein, nitrate, leukocyte esterase, urobilinogen, and bilirubin. If any parameter on the dipstick is abnormal, a urine sample should be sent to the central laboratory for quantitative measurement. If positive for protein and/or red blood cells, microscopic analysis will be performed by the central laboratory. Clinical laboratory testing at Screening Visit 1 will include hepatitis screen covering hepatitis B surface antigen (HBs Ag), hepatitis B surface antibody (HBs Ab), hepatitis B core antibody (HBc Ab), hepatitis C virus antibodies (HCV Ab), human immunodeficiency virus (HIV) screen (Anti-HIV-1 and HIV-2 antibodies) and anti-nuclear antibody (ANA). In case of results showing HBs Ag (negative), and HBc Ab (positive), an HBV DNA testing may be performed prior to randomization to rule out a false positivity if the Investigator believes the patient is a false positive, or to clarify the serological status if the investigator finds it unclear to interpret in absence of known HBV infection. In case of results showing HCV Ab (positive), an HCV RNA testing may be performed to rule out a false positivity, if the Investigator believes the patient is a false positive. Note: Anti-ds DNA antibody will be tested if ANA is positive ( $\geq 1:160$  titer). The blood sample for serum chemistry must be taken with the patient in fasting state which means no intake of any food or drink except for water for at least 8 hours (if the visit can only be done at a different time of the day and the patient is not fasting, then he/she should be advised to eat light food and the site should document that serum chemistry was not obtained under fasting conditions).
- o* Quantiferon gold should be collected for all patients at the Screening Visit 1. If the result is confirmed positive, the patient should be referred to an Infectious Disease specialist. Please refer to the central laboratory manual for additional details.

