#### 9.2.2 Disease-specific efficacy measures

##### 9.2.2.1 Spirometry

Spirometry should be performed in accordance with the American Thoracic Society (ATS)/European Respiratory Society (ERS) guidelines ([21](#)) and prior to administration of investigational product.

For prebronchodilator measured parameters, including FEV1, PEF, FVC and FEF 25%-75%, spirometry will be performed after a wash out period of bronchodilators according to their action duration, for example, withholding the last dose of salbutamol/albuterol or levosalbutamol/levalbuterol for at least 6 hours and withholding the last dose of LABA for at least 12 hours.

At all visits, spirometry will be performed preferably in the AM; PM is allowable in the exceptional circumstance when AM spirometry cannot be performed; spirometry should be done at approximately the same time at each visit throughout the study. The same spirometer and standard spirometric techniques, including calibration, will be used to perform spirometry at all visits and, whenever possible, the same person should perform the measurements.

Three measurements fulfilling the ATS acceptability and repeatability criteria should be obtained at every visit, if possible.

Reversibility is defined as an increase of the absolute FEV1 after administration of bronchodilator, and is measured by spirometry as postbronchodilator increase of FEV1 in percent of the prebronchodilator FEV1. After spirometry for measuring prebronchodilator FEV1, patients will receive 2-4 puffs of albuterol/salbutamol or levalbuterol/levosalbutamol from a primed MDI. Alternatively, and only if it is consistent with usual office practice (to be documented), reversibility may be performed using inhalation of nebulized albuterol/salbutamol or levalbuterol/levosalbutamol. The postbronchodilator spirometry may be repeated several times within 30 minutes after administration of bronchodilator. If the subject does not meet reversibility at Visit 1/Screening, up to 2 additional attempts during the screening period, each on a different day prior to Visit 2/Baseline, may be performed. When reversibility assessment is repeated during the screening period, the prebronchodilator FEV1 should again meet the inclusion criterion (I 03) of >40% of predicted normal.

Further details on spirometry will be available in a separate operational manual provided to the sites.

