The electronic diary/PEF meter is a handheld device used for daily recording of salbutamol/albuterol or levosalbutamol/levalbuterol use, asthma controller drug use, nocturnal awakenings due to asthma symptoms and AM and PM PEF, and recordings of patient's answers to the ACQ-5, AQLQ(S), and RQLQ questionnaires during the scheduled visits. These handheld devices are dispensed at Visit 1 (including instructions for use) and recorded information is downloaded from the devices on the other indicated days ([Section 1.2](#)). At Visit 14/EOT, recorded information is downloaded from the handheld devices and the devices are returned at EOS as the lastest.

- All eligible patients will be switched to the study-specific ICS/LABA background therapy, which consists of BID fluticasone/salmeterol inhalations, at clinically comparable doses (to each individual patient's prescribed ICS/LABA dose level prior to screening, ie, meeting the preprotocol definition of medium or high dose ICS/LABA; [Section 7.1](#)), as approved for region ([Section 8.2](#)):
  - Fluticasone/salmeterol – dry powder inhaler (DPI):
    - 1 puff of 250/50 mcg twice daily (BID) or
    - 1 puff of 500/50 mcg BID

OR

- Fluticasone/salmeterol – metered dose inhaler (MDI):
  - 2 puffs of 115/21 mcg (230/42 mcg) BID or
  - 2 puffs of 230/21 mcg (460/42 mcg) BID

OR

- Fluticasone/salmeterol – metered dose inhaler (MDI):
  - 2 puffs of 125/25 mcg (250/50 mcg) BID or
  - 2 puffs of 250/25 mcg (500/50 mcg) BID

- Dispense study-specific ICS/LABA medication (DPI or MDI).
- Remind patients to use fluticasone/salmeterol combination as background therapy medication. Instruct patient to record daily usage in the electronic diary.
- Remind patients to use salbutamol/albuterol or levosalbutamol/levalbuterol as reliever medication throughout the study. Instruct patient to record usage in the electronic diary.

- Remind patient to withhold albuterol or levalbuterol (if any) for at least 6 hours and LABA for at least 12 hours prior to next visit.
- Schedule a site visit for Visit 2, Day 1 and request patient to come at approximately the same time of day as this visit.

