#### ***10.1.2.1.1 Visit 2/Randomization/Baseline (Week 0/Day 1)***

- Record all concomitant medication use with start date and dose in eCRF; inquire about AEs/SAEs and background asthma therapy tolerability and compliance.
- Administer ACQ-5, AQLQ(S), and, only to patients with history of allergic rhinitis, RQLQ(S) via handheld device.
- Perform spirometry and measure exhaled nitric oxide:
  - Exhaled nitric oxide assessment is conducted prior to spirometry and following a fast of  $\geq 1$  hour.
  - Spirometry will be performed at approximately the same time of day as the last visit, prior to administration of IMP and after withholding the last dose of salbutamol/albuterol or levosalbutamol/levalbuterol for at least 6 hours and withholding the last dose of LABA for at least 12 hours. This will be verified before performing the measurements.
  - Prebronchodilator FEV1 should be determined.
  - Postbronchodilator FEV1 should be determined.
- Download electronic diary information from the handheld device, and remind patient to bring the device to the next visit.
- Perform physical examination.
- Perform urine pregnancy test (for women of childbearing potential)
- Measure vital signs (including systolic and diastolic blood pressure [mmHg], pulse rate [beats per minute], body weight [kg], respiratory rate [breaths per minute] and body temperature [ $^{\circ}\text{C}$ ]).

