2.4.5 Analyses of safety data

The summary of safety results will be presented by treatment group.

General common rules

All safety analyses will be performed on the safety population as defined in [Section 2.3.2](#), unless otherwise specified, using the following common rules:

- Safety data in patients who do not belong to the safety population will be listed separately
- The baseline value is defined as the last available value prior to the first dose of the IMP
- The potentially clinically significant abnormality (PCSA) values are defined as abnormal values considered medically important by the Sponsor according to predefined criteria/thresholds based on literature review and defined by the Sponsor for clinical laboratory tests, vital signs, and ECG (PCSA version dated May 2014, see [Appendix A](#))
- PCSA criteria will determine which patients had at least 1 PCSA during the treatment-emergent adverse event period, taking into account all evaluations performed during the treatment-emergent adverse event period, including nonscheduled or repeated evaluations. The number of all such patients will be the numerator for the on-treatment PCSA percentage
- The treatment-emergent PCSA denominator by group for a given parameter will be based on the number of patients assessed for that given parameter in the TEAE period by treatment group on the safety population.
- For quantitative safety parameters based on central laboratory/reading measurements, descriptive statistics will be used to summarize results and change from baseline values by visit and treatment group. Summaries will include the endpoint value. The endpoint value is defined as the value collected at or just prior to the last dose date + 14 days, or at end of treatment visit, whichever comes later. If this value is missing, this endpoint value will be the closest value prior to the last dose intake. The worst value is defined as the nadir and/or the peak post-baseline (up to last administration of IMP) according to the direction (minimum or maximum) of the abnormality as defined in the PCSA list
- The analysis of the safety variables will be essentially descriptive and no systematic testing is planned.

All safety values including unscheduled measurements will be assigned to the appropriate safety analysis visit window defined in [Section 2.5.4](#).

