2.4.5.4 Analyses of vital sign variables

The summary statistics (including number, mean, median, Q1, Q3, SD, minimum and maximum) of all vital signs variables (values and changes from baseline) will be calculated for each visit or study assessment (baseline, each post-baseline time point, and last on-treatment) by treatment group. For all parameters, mean changes from baseline with corresponding standard error will be plotted over time in each treatment group.

The incidence of PCSAs at any time during the TEAE period will be summarized by treatment group irrespective of the baseline level and/or according to the following baseline status categories:

- Normal/missing
- Abnormal according to PCSA criterion or criteria

Listings will be provided with flags indicating the PCSA values.

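### Vital signs follow the bronchodilator at baseline and at half of the later visits, so within-arm changes in pulse and blood pressure alternate with the spirometry schedule (minor; a wording change fixes it)

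*Protocol*

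**What the plan says.** **Order of assessments.** Protocol 10.1 gives a recommended order, to be followed where applicable and possible: questionnaires, ECG, procedures (FeNO, then spirometry and reversibility, then diary download), then "4. Safety and laboratory assessments", then study drug. That step does not name vital signs, but the visit lists in 10.1.2 place them after spirometry.

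**Bronchodilator.** At Visit 2 the list says "Postbronchodilator FEV1 should be determined", and section 9.2.2.1 says that after the pre-bronchodilator test "patients will receive 2-4 puffs of albuterol/salbutamol or levalbuterol/levosalbutamol from a primed MDI". The same post-bronchodilator line stands in the lists for V6, V8, V10, V12, V14, V15 and V17. The lists for V3, V4, V5, V7, V9, V11 and V13 have pre-bronchodilator spirometry only. SAP Table 7 agrees: its post-bronchodilator windows are baseline and Weeks 4, 6, 8, 10, 12, 20 and 32.

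**ECG.** The amendment 01 summary, in its entry for section 10.1, explains that the ECG was placed before lung function "in order to prevent potential effect of albuterol/salbutamol/levalbuterol/levosalbutamol administration on ECG tracing". Pulse and blood pressure were not moved with it.

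**Analysis.** SAP 2.4.5: "The baseline value is defined as the last available value prior to the first dose of the IMP". For vital signs this is normally Visit 2. SAP 2.4.5.4 adds that "mean changes from baseline with corresponding standard error will be plotted over time in each treatment group". The vital-sign criteria for potentially clinically significant abnormalities (PCSAs, SAP Appendix A) combine an absolute limit with a change from baseline. They count an event at any time in the treatment-emergent period.

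**Fasting.** Flow-chart note n: "The blood sample for serum chemistry must be taken with the patient in fasting state". If a patient is not fasting, the site documents it. The Visit 1 text on booking the next visit reads "Schedule a site visit for Visit 2, Day 1 and request patient to come at approximately the same time of day as this visit", with no mention of fasting.

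**The concern.** The baseline is taken under one condition and half of the later values under another. Change from baseline then contains a bronchodilator component that switches on and off with the visit schedule.

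From V6 this schedule also coincides with dosing. V6, V8, V10 and V12 are both dosing and bronchodilator visits, while the mid-interval visits V7, V9, V11 and V13 are neither. A reader of the by-visit plots who compares values one week after a dose with pre-dose values would be comparing bronchodilator-free with bronchodilator-exposed measurements.

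The sponsor has accepted this mechanism for the ECG. ECGs are recorded at only four visits (V1, V6, V14 and V17), whereas vital signs are taken at every visit except V16, so the denser cardiovascular series is the unprotected one.

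**Working it through.** The plan states no figure on this point, so there is none to reproduce.

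**Step 1: count visits (Protocol 10.1.2 lists; SAP 2.1.4.4 for vital signs).**
- Post-baseline visits with vital signs: V3 to V15 and V17, which is 13 + 1 = 14. On treatment (V3 to V14): 12.
- With a bronchodilator, as at V2: V6, V8, V10, V12, V14, V15, V17 = 7 (5 on treatment).
- Without: V3, V4, V5, V7, V9, V11, V13 = 7, all on treatment.
- Mismatch with baseline: 7/12 = 58% on treatment and 7/14 = 50% overall.

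**Step 2: expected offset.** Let *d* be the bronchodilator effect on pulse. With no true change, the expected change from baseline is
- without bronchodilator: μ - (μ + *d*) = -*d*
- with bronchodilator: (μ + *d*) - (μ + *d*) = 0.

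With vital signs before the bronchodilator at every visit, it is 0 throughout.

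**Step 3: effect on heart-rate PCSAs.** The rules are ≥120 bpm with an increase ≥20, and ≤50 bpm with a decrease ≥20, at any visit. The documents give neither *d* nor the SDs, so these are assumptions: *d* = 0, 3, 5 or 10 bpm; mean / between-patient SD / within-patient SD = 75/10/7 or 80/11/9 bpm. Each scenario simulates 400,000 patients with no drug effect and all 14 visits complete. The table gives the percentage of patients with at least one event.

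| Mean/SDs | *d* | Mean change, 7 visits without bronchodilator | High HR: order as written | High HR: vital signs first | Low HR: order as written | Low HR: vital signs first |
|---|---|---|---|---|---|---|
| 75/10/7 | 0 | 0.0 | 0.04 | 0.04 | 2.8 | 2.8 |
| | 3 | -3.0 | 0.07 | 0.05 | 3.1 | 2.8 |
| | 5 | -5.0 | 0.09 | 0.04 | 3.5 | 2.8 |
| | 10 | -10.0 | 0.26 | 0.05 | 5.0 | 2.7 |
| 80/11/9 | 0 | 0.0 | 1.2 | 1.2 | 5.2 | 5.2 |
| | 3 | -3.0 | 1.4 | 1.1 | 5.1 | 5.3 |
| | 5 | -5.0 | 1.8 | 1.2 | 5.3 | 5.3 |
| | 10 | -10.0 | 3.2 | 1.2 | 6.0 | 5.3 |

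Mean change at the seven bronchodilator visits is zero in every row. Variation down the vital-signs-first columns is simulation noise.

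**Step 4: direction.** At visits without a bronchodilator the increase condition is harder to meet. At visits with one, *d* cancels from the change but still lifts the absolute value towards 120. Over all visits the second effect outweighs the first, so high-heart-rate counts rise. In the most extreme row, per arm of 60, this is 0.032 × 60 = 1.9 patients against 0.012 × 60 = 0.7, about one extra. Blood pressure was not simulated, but its criteria have the same two-part form.

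**Step 5: fasting text.** The booking lines carry a fasting reminder for V6, V10, V14, V15 and V17 (5 of 5 later chemistry visits) but not for V2. The blood-sampling lines mention fasting at V10, V14, V15 and V17 but not at V2 or V6. Note n covers all of them.

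**The case against.** The strongest reply is that the offset is common to all four randomized, blinded arms. Safety is summarized descriptively against concurrent placebo, so the expected between-arm difference in mean change is zero. This largely stands. Cancellation is not quite exact: patients who stop early have an end-of-treatment visit with post-bronchodilator spirometry, and SAP Table 8 assigns vital signs to windows by study day. Such values can fall in windows that are otherwise bronchodilator-free, more often in arms with more loss of asthma control. That effect is probably small.

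Three further replies also carry weight. The order is only recommended. ECG heart rate, with its own PCSA criteria at V6, V14 and V17, is measured before the bronchodilator. Within-arm trends already move with the withdrawal of background therapy from Week 4. None of these removes the alternation in the plotted vital-sign changes if sites follow the lists as written.

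A reader might go further and infer any of the following, which the documents do not support:
- **That tachycardia would be missed.** This is true of the change condition alone at visits without a bronchodilator. Under the full any-visit rule the high-heart-rate count rises.
- **That the V2 chemistry baseline is planned as unfasted.** Note n requires fasting with no exception for V2, and non-fasting samples must be documented. The glucose PCSA has separate fasted and unfasted limits and no change-from-baseline condition.
- **That blood sampling also needs to move.** Every later chemistry visit (V6, V10, V14, V15, V17) is a bronchodilator visit, as V2 is, so conditions already match.
- **That V2 differs from most later visits.** For vital signs it differs from 7 of 14 overall, and from a narrow majority (7 of 12) only on treatment.

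**Conclusion.** The point holds for vital signs, as a minor one. If the order is followed as written, the Visit 2 baseline and seven later visits are measured after a bronchodilator and seven are not. This puts an alternating offset, equal in size to the bronchodilator effect, into within-arm changes in pulse and blood pressure, and it can alter PCSA counts. For assumed pulse effects of 3 to 10 bpm the offset is -3 to -10 bpm at the seven unmatched visits. High-heart-rate PCSAs rise modestly, from 0.04-0.05% to 0.07-0.26% or from 1.1-1.2% to 1.4-3.2% depending on the assumed mean and SDs. Low-heart-rate PCSAs change little or rise, up to 5.0% or 6.0%. The effect sizes and SDs are assumptions, while the visit counts come from the documents. Little or no bias between arms is expected. The fasting matter is an editorial mismatch between visit text and flow chart.

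**What to change.** In section 10.1 and in each visit list, place vital signs with the ECG, before FeNO and spirometry. Blood sampling can stay where it is.

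As an editorial correction, reconcile the visit text with flow-chart note n: add the fasting reminder to the line in 10.1.1 that books Visit 2, and to the blood-sampling lines for V2 and V6.

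The cost is protocol wording and a slightly reordered visit at site. No procedure, visit or analysis is added, and the SAP needs no change.

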#### **10.1.1 Visit 1/Screening (Week -4 to Week 0 [zero], Day -28 to Day 0) – Screening Visit**

Following a discussion of participation in the clinical trial, informed consent must be obtained and documented. These steps precede any study procedures. The visit schedule should be adhered to within the  $\pm$ 3 day visit window allowed during the treatment phase of the study.

The following procedures will then be performed:

- Call IVRS/IWRS to assign patient number and register screening visit.
- Interview to collect patient demographic information, asthma history (including smoking habits), previous medical history and surgical history, and prior and concomitant medications. Inquire about AEs/SAEs.
- Administer ACQ-5 via handheld device
- Perform 12-lead ECG

- Review entry criteria to assess eligibility ([Section 7.1](#) for details) , with special attention to verify the following:
  - Existing treatment with medium to high dose ICS ( $\geq 250$  mcg of fluticasone propionate BID or equipotent ICS daily dosage to a maximum of 2000 mcg/day of fluticasone propionate or clinically comparable) in combination with a LABA as second controller for at least 3 months with a stable dose  $\geq 1$  month prior to Visit 1.
- Perform Spirometry (review eligibility criteria) and measure exhaled nitric oxide:
  - Exhaled nitric oxide assessment is conducted prior to spirometry and following a fast of  $\geq 1$  hour.
  - Spirometry will be performed after a washout period of bronchodilators according to their action duration, for example, withholding the last dose of salbutamol/albuterol or levosalbutamol/levalbuterol for at least 6 hours and withholding the last dose of LABA for at least 12 hours. This will be verified before performing the measurements.
  - Patients with reversibility of at least 12% and 200 mL in FEV1 after administration of 2 to 4 puffs (200-400 mcg) of albuterol/salbutamol or levalbuterol/levosalbutamol during screening or documented history of a reversibility test that meets this criteria within 12 months prior to Visit 1 or documented positive response to methacholine challenge (a decrease in FEV by 20% [PC20] of  $<8$ mg/mL) within 12 months prior to Visit 1/Screening is considered acceptable to meet this inclusion criterion.

Note: If the subject does not meet the qualifying criteria for reversibility at Visit 1/Screening, up to 2 additional attempts during the screening period, each on a different day prior to Visit 2/Baseline, may be performed. When reversibility assessment is repeated during the screening period, the prebronchodilator FEV1 should again meet the inclusion criterion ([I 03](#)) of  $>40\%$  of predicted normal.

- Perform physical examination (refer to [Section 9.2.3.1.1](#)). Complete physical examination will include skin, nasal cavities, eyes, ears, respiratory, cardiovascular, gastrointestinal, neurological, lymphatic, and musculoskeletal systems.
- Measure vital signs (including systolic and diastolic blood pressure [mmHg], heart rate [beats per minute], respiration rate [breaths per minute], body temperature [ $^{\circ}$ C], body weight [kg], and height [cm]).

After determination of preliminary eligibility:

- Obtain blood samples for screening clinical laboratory (see [Section 9.2.3.4](#) for details) determinations: hematology and serum chemistry.
- Obtain blood samples for screening serology: HBs Ag, HBs Ab, HBc Ab, hepatitis C virus antibodies (HCV Ab), anti-HIV-1 and HIV-2 antibodies, and ANA.
- Obtain urine sample for urinalysis.
- Quantiferon gold testing.

Note: If the result is confirmed positive, the patient should be referred to an Infectious Disease specialist.

- Obtain serum  $\beta$ -hCG pregnancy test if female of childbearing potential
- Perform blood sampling for the following tests:
  - Biomarker set: blood eosinophils and neutrophils, total IL33, sST2, calcitonin, PARC, eotaxin-3, total IgE and periostin (refer to [Section 9.3.2.4](#)),
  - Optional: Sample for RNA panel testing for those patients who have consented to it
  - Optional: Archival of serum and plasma for those patients who have consented to Future Use of Specimens (refer to [Section 9.4](#))
- Dispense electronic diary/PEF meter handheld device, provide instructions for daily use, and remind patient to bring the device to the next visit.

The electronic diary/PEF meter is a handheld device used for daily recording of salbutamol/albuterol or levosalbutamol/levalbuterol use, asthma controller drug use, nocturnal awakenings due to asthma symptoms and AM and PM PEF, and recordings of patient's answers to the ACQ-5, AQLQ(S), and RQLQ questionnaires during the scheduled visits. These handheld devices are dispensed at Visit 1 (including instructions for use) and recorded information is downloaded from the devices on the other indicated days ([Section 1.2](#)). At Visit 14/EOT, recorded information is downloaded from the handheld devices and the devices are returned at EOS as the lastest.

- All eligible patients will be switched to the study-specific ICS/LABA background therapy, which consists of BID fluticasone/salmeterol inhalations, at clinically comparable doses (to each individual patient's prescribed ICS/LABA dose level prior to screening, ie, meeting the preprotocol definition of medium or high dose ICS/LABA; [Section 7.1](#)), as approved for region ([Section 8.2](#)):
  - Fluticasone/salmeterol – dry powder inhaler (DPI):
    - 1 puff of 250/50 mcg twice daily (BID) or
    - 1 puff of 500/50 mcg BID

OR

- Fluticasone/salmeterol – metered dose inhaler (MDI):
  - 2 puffs of 115/21 mcg (230/42 mcg) BID or
  - 2 puffs of 230/21 mcg (460/42 mcg) BID

OR

- Fluticasone/salmeterol – metered dose inhaler (MDI):
  - 2 puffs of 125/25 mcg (250/50 mcg) BID or
  - 2 puffs of 250/25 mcg (500/50 mcg) BID

- Dispense study-specific ICS/LABA medication (DPI or MDI).
- Remind patients to use fluticasone/salmeterol combination as background therapy medication. Instruct patient to record daily usage in the electronic diary.
- Remind patients to use salbutamol/albuterol or levosalbutamol/levalbuterol as reliever medication throughout the study. Instruct patient to record usage in the electronic diary.

- Remind patient to withhold albuterol or levalbuterol (if any) for at least 6 hours and LABA for at least 12 hours prior to next visit.
- Schedule a site visit for Visit 2, Day 1 and request patient to come at approximately the same time of day as this visit.

